Comparison groups of adults with: i) active AUD and no HCV (n = 30) and ii) no AUD or HCV (n = 30) will also be studied. Thus, we will enroll 120 participants into the following four study groups: 1) AUD+/HCV+, 2) AUD-/HCV+, 3) AUD+/HCV- and 4) AUD-/HCV-. Evaluations will incorporate neuropsychiatric assessments, brain imaging [resting state (rs) magnetic rsMRI, functional (f) MRI (fMRI), and diffusion tensor imaging], and laboratory methods [e.g., multicolor flow cytometry, quantitative polymerase chain reaction (PCR), and multiplex immunoassays] to assess the interactive effects of alcohol use on brain and immune function [e.g. changes in T cell response and inflammatory cytokines, such as TNF- α] that contribute to viral persistence and neuropsychiatric impairments. We will use general linear models to assess whether average change in the response (e.g., neuropsychiatric and immunologic outcomes) over six months between post- and pre-DAA therapy for each subject differs among the four groups—either due to AUD, HCV, or the potential interaction of these factors—after controlling for other subject-level covariates that remain constant (or nearly so) over the 6 months (e.g., age, sex). Variables that could meaningfully vary over time (e.g., TLFB score) will be summarized in terms of a difference and then included as a covariate.

Table 1. Overview of human subjects procedures, including research visits and HCV treatment schedule^a (as per standard of care)

Weeks					
-2	0	12	18	24	26
Baseline visits (wks -2-0)^c		DAA therapy completion (wk 12)	- Check-in w/participants ^b	SVR assessment (wk 24; 12-wk post DAA therapy)	
- Clinical interview		ETR assessment (wk 12)		6-month follow-up visits (wks 24-26)^c	
- Neuropsychiatric assessment		- Check-in w/participants ^b		- Neuropsychiatric assessment	
- Specimen collection				- Specimen collection	
- Neuroimaging evaluation		DAA therapy initiation (wk 0)		- Neuroimaging evaluation	

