^aIn addition to the visits outlined in this table, Veterans receiving DAA therapy participate in two standard, follow-up clinic appointments at weeks 4 and 8 (typically 15-20 min appointments). Note: *The follow-up clinic is a large multidisciplinary clinic comprised of doctors, fellows, nurse practitioners, liver clinic pharmacist and pharmacy students. Patients do not usually see the same clinician at the follow-up appointments that they saw at the start appointment. In addition, approximately 50% of individuals started on DAA therapy are followed in the pharmacist phone clinic, and the week 4 and 8 appointments are by phone (~10 min calls).* The potential impact of these additional interactions on study outcomes is discussed in Expected outcomes and alternative considerations. ^bClinical research staff will check-in with participants (phone contact) to assess general well-being, complete the TLFB (Sobell et al., 1996), and confirm schedules for follow-up visits.

^cParticipants will be paid \$125 for the baseline visits (\$75 for visit 1 [clinical interview, neuropsychiatric assessment, specimen collection] and \$50 for visit 2 [specimen collection, neuroimaging evaluation]). Subjects who participate in the 6-month follow-up visits will receive an additional \$125 (\$75 for visit 3 [neuropsychiatric assessment, specimen collection] and \$50 for visit 4 [specimen collection, neuroimaging evaluation]). In sum, subjects can earn \$250 total if they complete all of the scheduled visits.

Enrollment procedures. Prior to enrollment, a phone screening will be conducted by study staff to ensure that Veterans are interested in participating and meet eligibility criteria. Following screening, interested Veterans will be scheduled for a first study visit to review consent materials either in person at the VAPORHCS, by telephone, or VA approved teleconferencing software (i.e., VA Video Connect [VVC] or non-public facing technologies [i.e., Cisco WebEx, Skype for Business, Zoom for Healthcare, Doxy.me]).

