 - NAB Judgment - measure of everyday problem-solving/executive function
 - Categories – measure of mental flexibility and categorization
 - Word Generation – measure of initiation and mental flexibility.

Questionnaire battery. AUD Identification Test-C [AUDIT-C; 3-item screening tool to be administered at baseline only (Bush et al., 1998)]; Severity of Dependence Scale (SDS) (Gossop et al., 1997, Gossop et al., 1995); Alcohol Timeline Followback (TLFB) (to be administered in-person at pre- and post-DAA therapy study visits, as well as over the phone at weeks 12 and 18). In addition to in-person interviews, the TLFB has demonstrated reliability and validity over the phone (Sobell, 1992, Sobell et al., 1996); Clinical Institute Withdrawal Assessment for Alcohol scale, revised (CIWA-Ar) (Sullivan et al., 1989); Visual Analogue Scale (rates level of craving for alcohol over the past 24 hours on a scale of 0 to 100); Beck Depression Inventory, Second Edition (BDI) (Beck, 1996); Generalized Anxiety Disorder Inventory (GAD) (Argyropoulos et al., 2007) and PCL-C (Weathers et al., 1994); Fatigue Severity Scale (FSS) (Krupp et al., 1989); Brief Pain Inventory, Short Form (BPI) (Cleeland and Ryan, 1994), and Sickness Impact Profile (Bergner et al., 1981).

Specimen collection and laboratory measures. At study visits, oral fluid is collected and used toward HIV antibody screening by OraQuick (OraSure Technologies Inc.) or similar "in-home" oral swab test and alcohol testing by Alco-Screen (Chemetrics, Inc.) or similar alcohol saliva test. Urine is collected and used for urine alcohol [*i.e.*, ethyl glucuronide (EtG) levels] and drug analysis and pregnancy tests. EtG assessments are done with EtG Alcohol Test Dip Cards (Rapid Exams Inc.). Drug analysis and pregnancy tests are conducted using 5 panel Drug Screen Cups (Rapid Exams Inc.) and human chorionic gonadotropin (hCG) urine dip card tests (Rapid Exams Inc.), respectively. Blood is collected by a trained phlebotomist or trained VA research personnel in four, 8 mL capacity Cell Preparation Tubes (CPTs, BD Biosciences) for planned experiments (≤ 32 mL of blood is collected at both the initial and 6-month study visits). If not already obtained per standard care for HCV, blood samples (≤ 23.5 mL) may also be collected to obtain HCV viral load, liver enzyme levels,

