Immune cell phenotype and function. PBMCs collected before and after DAA therapy will be used to evaluate phenotypic and functional changes in memory T cells (central, effector, and transitional) and macrophages that regulate viral suppression and persistence. Cell phenotype will be determined using flow cytometry, as previously described [e.g., (Loftis et al., 2016, Wilhelm et al., 2013)]. Briefly, single-cell suspensions of human PBMCs will be stained to identify and analyze viable cell phenotypes, including subsets of CD4+ and CD8+ T cells (e.g., effector and regulatory cell subpopulations), programmed cell death 1+ (PD-1+) cells, and activated macrophages (CD45^{hi}CD11b+ cells). Immune cell function will be assessed by measuring cell proliferation and inflammatory factors secreted from cells stimulated *in vitro*, as described in methods reviewed by the VA Subcommittee on Research Safety (SRS). Given that chronic viral infections and AUD are associated with phenotypic and functional impairments in CD4 and CD8 T cell subsets and the PD-1 inhibitory receptor [measure of an "exhausted" phenotype; e.g., (Utzschneider et al., 2016)], we will focus on these immune cells and signaling pathways. Our analyses will additionally be guided by a recent cross-sectional study of patients with AUD which found significant alterations in CD8+ and CD4+ T subpopulations in patients with AUD, as compared to healthy controls (Zuluaga et al., 2016).

Neuroimaging.* Following the neuropsychiatric study visit, all eligible participants are scheduled for a separate neuroimaging study visit. Neuroimaging may be omitted for medical reasons or if determined by study team to not be in the subject's best interest. Subjects, well characterized with respect to their substance use, will then be evaluated with fMRI tasks (BART and MID), rsMRI, high resolution anatomical MRI, standard DWI and high angular resolution diffusion imaging (HARDI). Breathalyer tests, alcohol withdrawal symptom scales, urine alcohol and drug screens, and pregnancy tests will be administered at the neuropsychiatric study visits and the imaging evaluations. The neuroimaging protocol will take approximately one hour and will include the Balloon Analogue Risk Task (BART) and Monetary Incentive Delay Task (MID).

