Diffusion-Weighted Imaging: DTI preprocessing will be performed using the DTI preprocess script (Takuya Hayashi, Center for Life Science Technologies, RIKEN, Kobe, JP) for FSL [(Smith et al., 2004) FMRIB, Oxford]. Scans will be corrected for eddy current distortion and motion. B_0 inhomogeneity distortion will be corrected using a B_0 field map (magnitude and phase) in FSL's fugue. DTI estimates (FA, λ_{1-3} , V_{1-3} , MD) will be calculated using DTIFIT. Voxelwise statistical analysis will be performed with TBSS (Smith et al., 2006) and nonlinear registration to the FMRIB58_FA common space will be conducted. Each subject's aligned FA data will be projected onto a mean skeleton. Voxelwise cross-subject statistics will be performed with FSL's *Randomise* with threshold-free cluster enhancement (TFCE).

Voxel-Based Morphometry: Structural images will be analyzed with FSL-VBM (Douaud et al., 2007) an optimized VBM protocol (Good et al., 2001) carried out with FSL (Smith et al., 2004). Images will be brain-extracted and tissue segmented, registered to the MNI-152 standard space using non-linear registration (Andersson et al., 2007), and flipped along the x-axis to create a left-right symmetric, study-specific gray matter template and modulated with a voxel-wise division by the Jacobian determinant of the non-linear transformation matrix to correct for local expansion or contraction. The modulated gray matter images will be smoothed with an isotropic Gaussian kernel with a sigma of 3 mm (FWHM = 7 mm). Group contrasts will be tested with FSL's *Randomise*, a permutation-based non-parametric procedure.

Statistical analyses and power. Statistical analyses for the project will be performed by the research team and the Biostatistics and Design Program at OHSU. All data sent to OHSU for statistical analysis will be coded.

Neuropsychiatric and laboratory measures. We plan to calculate the change in the response over six months between post- and pre-DAA therapy for each subject and use general linear models (GLMs) to assess whether average change differs among the four groups—either due to AUD, HCV, or the

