To test hypotheses for aims 1 and 2, 120 Veterans will be recruited to participate in a prospective study that will evaluate patients with HCV before and after DAA therapy. Participants will be enrolled in the study for a total of six months			
Months 1-3: Obtain IRB and other regulatory approvals; Apply for Certificate of Confidentiality; Train staff in protocol and data analysis.	Months 13-15: Enroll and conduct baseline study visits; Complete 6-month follow-up visits for ~10 participants	Months 25-28: Complete 6-month follow-up visits for ~10 participants.	Months 37-40: Complete 6-month follow-up visits for remaining participants (goal: n = 120 completed by month 40); Conduct flow cytometry analysis of cryopreserved PBMCs.
Month 4: Begin recruitment of subjects using existing relationships with clinics at the VAPORHCS; Enroll and conduct baseline study visits for 4 participants.	Months 16-19; Enroll and conduct baseline study visits; Begin analyzing behavioral data and continue to conduct analysis of individual neuroimaging data; Complete 6-month follow-up visits for ~14 participants.	Months 29-35: Complete 6-month follow-up visits for ~30 participants; Assess drop-out rates and intensify follow-up efforts, if needed.	Month 41-42: Perform multiplex plasma sample testing for immune activation biomarkers; Submit abstract for conference presentation.
Months 5-9: Enroll and conduct baseline study visits for 30 participants at a rate of ~1-2 participants per week.			

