received but not reviewed the letter, the researcher may ask if they are interested in hearing more about the study or receiving more information. After answering their questions, the researcher will schedule an Initial Study Visit for those who state they are interested in participating. If the Veteran has not received the letter, the researcher will only ask permission to send a second letter and confirm the individual's address; no other information will be requested at that time.

An appointment confirmation letter will be mailed to a participant after they have scheduled their initial visit. An appointment confirmation letter will also be sent prior to the week 24 visit. If a participant is enrolled in the study and not returning phone calls to schedule additional research visits, a no-show letter will be sent in the mail asking the participant to contact the research coordinator to discuss their interest in their continued involvement in the research study. If the research coordinator does not hear back from the participant within two weeks of sending the letter, the participant will be disenrolled from the research study.

Reminder phone calls will be made the day prior to scheduled on-site appointments. During reminder calls, study team will ask participants if they have recently had any recent exposure and/or symptoms of COVID-19. If a participant suggests that they might be experiencing symptoms or have had a known exposure to COVID-19, we will offer information on COVID-19 testing and self-isolation and postpone the study visit for at least two weeks following exposure or until symptoms are completely resolved. When the participant arrives for their appointment, their temperature will be taken using a digital thermometer and the same screening questions will be asked again before beginning the appointment. The participant will be sent home with the same information on testing and self-isolation upon indication or disclosure of any symptoms or exposure to someone with confirmed or suspected COVID-19. Also during confirmation calls, participants will be informed that masks are required to be worn during their entire visit. If a subject does not have access to a mask, the study team will provide one. Subjects will be instructed on how to properly care for their masks if they need to remove them during the study visit.

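### The no-show rule can disenrol a silent participant weeks before the week 24-26 outcome visit, causing avoidable loss of change scores that the plan has no method to handle

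*Combined protocol and SAP*

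**What the plan says.** The rule stands near the end of Subject Identification/Recruitment. It concerns an enrolled participant who is "not returning phone calls to schedule additional research visits, a no-show letter will be sent in the mail". If the coordinator "does not hear back from the participant within two weeks of sending the letter, the participant will be disenrolled from the research study". The text gives no minimum number of calls, no week from which the rule applies, and no link to the outcome visit. It makes no distinction between the four groups.

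The other relevant statements are:

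- **Outcome visit.** Table 1 places the "6-month follow-up visits (wks 24-26"). This is the only full assessment after baseline.
- **Contacts in between.** Table 1, footnote b, has staff telephone participants to ask about well-being, "complete the TLFB (Sobell et al., 1996), and confirm schedules for follow-up visits". The Questionnaire battery paragraph dates these calls: the TLFB is taken at the study visits "as well as over the phone at weeks 12 and 18".
- **Second baseline visit.** After the neuropsychiatric visit, "all eligible participants are scheduled for a separate neuroimaging study visit".
- **Analysis.** Under Statistical analyses and power: "We plan to calculate the change in the response over six months between post- and pre-DAA therapy for each subject". Group differences in that change are then modelled.
- **Retention.** Table 3 sets a goal of 120 completed by month 40, and Study Population enrols 120. Table 3 also says: "Assess drop-out rates and intensify follow-up efforts, if needed".

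**The concern.** The rule ends participation by a clock that starts with the letter, whatever the distance to the outcome visit. A participant who is hard to reach in mid-study, but who would have attended at week 24, can be closed out while the outcome is still obtainable. Because the analysis variable is a within-person change, that participant then contributes nothing to the main models.

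The plan does not cushion this. It allows for no drop-out and states no missing-data method. The only shortfall the Power paragraph considers is about 3 to 6 participants with HCV who may not reach SVR, which is not loss to follow-up.

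The protocol is also more persistent with strangers than with its own participants. A prospective recruit who leaves a letter unanswered for two weeks is telephoned, and one who never received it may be sent a second. An enrolled participant, with baseline data already collected, is removed after the same interval.

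Two things are at stake: precision, through avoidable loss, and possibly bias in the AUD comparisons of Aim 2 if those who fall silent differ by AUD status or by the course of their drinking.

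**Working it through.** **1. Timing.** Inputs: two weeks from letter to disenrolment (the rule), check-ins at weeks 12 and 18 (Questionnaire battery), outcome window weeks 24-26 (Table 1). Assumption: the unanswered contact counts as the trigger and the letter goes out in the same week *c*. Then disenrolment falls at *c* + 2, the window opens 24 − (*c* + 2) weeks later, and it closes 26 − (*c* + 2) weeks later.

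| Unanswered contact | Disenrolled at | Weeks to opening | Weeks to closing |
|---|---|---|---|
| Week 12 check-in | 14 | 10 | 12 |
| Week 18 check-in | 20 | 4 | 6 |
| Scheduling of baseline visit 2, about week 0 | 2 | 22 | 24 |

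The last row is what the literal wording permits, since baseline visit 2 is also a further visit to be scheduled.

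**2. The plan's own power.** Inputs: 30 per group, 80% power for a main effect of 0.51 SD at the 0.05 level and for an interaction of 0.91 SD at the 0.10 level (Power paragraph); two-sided tests assumed.

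- Main effect: SE = √(1/60 + 1/60) = 0.183 SD. 0.51/0.183 = 2.79, and Φ(2.79 − 1.96) = 0.80. Noncentral t with 116 df gives 0.791.
- Interaction: SE = √(4/30) = 0.365 SD. 0.91/0.365 = 2.49, and Φ(2.49 − 1.645) = 0.80. Noncentral t gives 0.798.

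The stated figures reproduce, with every enrolled participant analysed.

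**3. Power under assumed loss.** The documents give no drop-out rate, so these are scenarios for total loss. The rule's own share is smaller: the fraction disenrolled multiplied by the fraction of those who would have attended. With *a* per AUD+ group and *b* per AUD− group, SE(main) = √(1/2*a* + 1/2*b*), SE(interaction) = √(2/*a* + 2/*b*), df = 2*a* + 2*b* − 4.

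| Loss AUD+ / AUD− | *a* / *b* | Main effect 0.51 SD | Interaction 0.91 SD |
|---|---|---|---|
| 0% / 0% | 30 / 30 | 0.791 | 0.798 |
| 10% / 0% | 27 / 30 | 0.769 | 0.778 |
| 20% / 0% | 24 / 30 | 0.742 | 0.755 |
| 20% / 10% | 24 / 27 | 0.721 | 0.737 |
| 20% / 20% | 24 / 24 | 0.696 | 0.715 |
| 30% / 10% | 21 / 27 | 0.689 | 0.709 |

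**4. Bias, if loss is related to outcome.** The unadjusted completer mean of a group is shifted by (share lost) × (completer mean − mean of those lost). Both factors are assumed:

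- 10% lost, 0.25 SD apart: 0.10 × 0.25 = 0.025 SD, or 5% of 0.51
- 20% lost, 0.5 SD apart: 0.20 × 0.5 = 0.10 SD, or 20% of 0.51
- 30% lost, 1.0 SD apart: 0.30 × 1.0 = 0.30 SD, or 59% of 0.51

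A shift common to both AUD+ groups passes in full to the AUD main effect and cancels in the AUD × HCV interaction. A shift in one AUD+ group only passes by half to the main effect and in full to the interaction. The documents do not say which scenario, if any, applies.

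**The case against.** The rule is the same for all four groups, and nothing in the documents gives retention by AUD status. The nearest text, in the section on relevance to Veterans' health, links alcohol use to completion of treatment, not to staying in a study. A reader might infer that the rule in itself creates outcome-related loss in the AUD groups. The documents do not support that. The rule costs data only from people who ignore calls and a letter and would still have come; the rest are lost anyway.

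The timing is an inference too. The trigger speaks of calls in the plural, and the rule follows closely on a sentence about the week 24 confirmation letter, so it may have been meant to operate around that visit. Nothing says that one missed check-in suffices, or that the letter goes out at once.

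A reader might also infer that the lost AUD+ participants are those who fared worst, that the AUD+ groups therefore look too good, and that Aim 2 is weakened. This does not fit every outcome. Table 2 projects larger reductions in the AUD+ groups for depression (AUD main effect −5.1) and alcohol use (−26.5). Losing the worst AUD+ participants would exaggerate those effects, while shrinking the projected AUD deficit on the cognitive rows. The models may also carry TLFB change as a covariate, which would remove some of any bias driven by drinking, though not for TLFB itself.

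Finally, Table 3's plan to intensify follow-up is a study-level review. It pulls the other way from the rule but does not contradict it, and the text does not expressly bar a return after disenrolment.

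All of this stands against firm claims of bias, direction or date. It does not answer the narrower point: as worded, the rule may end follow-up before the outcome is due, and the plan does not say what happens to the missing change score.

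**Conclusion.** The point holds as a conditional one and as an inexpensive improvement. What the documents establish is a disenrolment rule of one letter and two weeks, unconnected to the week 24-26 window, combined with an analysis that needs both values, a completion target equal to enrolment, and no missing-data method. Avoidable loss of outcomes is therefore possible.

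The figures of 10 and 4 weeks before the window rest on a missed check-in being the trigger and on the letter going out that week; the wording also permits earlier disenrolment. The power losses in the table rest on assumed drop-out. Differential loss by AUD status or drinking course is plausible, but neither its existence nor the direction or size of the resulting bias can be derived from the documents.

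**What to change.** Replace the two-week disenrolment with wording such as: *Non-response to calls or letters does not end participation; contact attempts continue, and the week-24 visit is offered, until the follow-up window closes, unless the participant withdraws or asks not to be contacted.*

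In the analysis section, add that losses are reported by group, week and reason. Add a sensitivity analysis for missing change scores, for example imputation from group, baseline value and any TLFB data from the check-ins, repeated with the imputed changes in the AUD+ groups shifted in either direction by a stated range such as 0.25 to 1.0 SD. This second part remains possible even if follow-up has ended.

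The cost is a few more calls and letters by existing staff and a possible IRB amendment. Files would stay open about 6 to 12 weeks longer in the check-in scenarios, and up to about 24 weeks longer for someone who goes silent before baseline visit 2.
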